5.7.3 Plasma Concentrations of Concomitant AEDs

Blood sampling for AEDs will be performed at Visit 3 (Day 1), Visit 5, Visit 7, Visit 9 and Visit 10 (end of treatment) of the blinded phase. For each AED, plasma concentrations will be summarized by treatment arm at each visit for patients in the safety analysis set.

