## 2.3 Exploratory

#### **Blinded Phase:**

- To evaluate the effect of GWP42003-P on TSC-associated neuropsychiatric disorders (TAND), including cognitive and behavioral function and autistic features compared with placebo.
- To determine the pharmacokinetics (PK) of CBD, and its major metabolites following single and multiple doses of GWP42003-P.
- To evaluate the effects of GWP42003-P on plasma concentrations of concomitant antiepileptic drugs (AEDs), if applicable.

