#### **PK (Double-blind only):**

- The plasma concentrations will be summarized by time window for CBD and its major metabolites following single and multiple doses of GWP42003-P.
   Where data allows, the area under the plasma concentration curve (AUC0-t) from time zero to the last measurable time-point will be calculated.
- Plasma concentrations of concomitant AEDs before and after treatment with GWP42003-P, where available.

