## 8.2 Concomitant Therapy

It is theoretically possible that GWP42003-P may modify the metabolism of other drugs (including AEDs) administered concurrently and there remains the possibility of pharmacological interactions between GWP42003-P and other concurrently administered drugs. Doses of any concomitant AEDs must have been stable for at least four weeks prior to screening and must remain stable throughout the blinded study period. If during the blinded or OLE phase plasma concentrations of concomitant AEDs are found to be altered following administration of IMP, or if there are side-effects suspected of being related to an elevation in the concomitant AED concentration, the investigator must contact the GW medical monitor to discuss best management. Decisions should be based on clinical symptoms and not plasma levels of AEDs. Further information on drug interactions can be found in the IB. Concomitant AED dose reductions are permitted on clinical grounds (e.g., due to AEs or transaminase elevations **not meeting** withdrawal criteria specified in Section 10 and Section 12.8) following discussion with the GW medical monitor.

Additional new AEDs (including oral mTOR inhibitors) are not allowed to be added during the randomized phase of the trial but may be considered on a case-by-case basis for the OLE phase in accordance with local licensing and after consultation with the GW medical monitor.

The use of rescue medication is allowed when necessary. Any medication, other than the IMP, taken during the study must be recorded on the Case Report Form (CRF).

Any non-pharmacological therapies (e.g., ketogenic diet, vagus nerve stimulation) must also be stable up to four weeks prior to screening and throughout the duration of the study.

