#### 9.2.9.2 Determination of Plasma Concentrations of Concomitant Antiepileptic Drugs

Plasma concentrations of concomitant AEDs will be assessed at Visits 3, 5, 7, 9 and 10/ the Withdrawal visit (if possible) during the blinded phase and at Visits B2, B3, B4 and all subsequent Assessment Visits during the OLE. Samples will be collected for all patients provided that the risk/benefit outcome is favorable in the investigator's opinion. At each visit, blood samples will be taken prior to administration of IMP. Patients will be instructed to record the dosing time of their concomitant AEDs in the diary.

Additional blood samples may be taken for AED monitoring if there is a suspicion of changes in AED levels, with the aim to keep the AED plasma levels within the patient's therapeutic level. AED doses should be adjusted, as appropriate, following discussion with the GW medical monitor in order to maintain stable AED plasma concentrations.

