#### 13.6.4 Pharmacokinetics

Plasma concentrations for CBD and its major metabolites, following single and multiple doses of GWP42003-P will be summarized by treatment group. Estimates of PK parameters will also be summarized using the appropriate statistics.

Where available, plasma concentrations of concomitant AEDs will be summarized.

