2.3 Exploratory Objectives

Blinded Phase:

- To evaluate the effect of GWP42003-P on TSC-associated neuropsychiatric disorders (TAND), including cognitive and behavioral function and autistic features compared with placebo.
- To determine the pharmacokinetics (PK) of CBD, and its major metabolites following single and multiple doses of GWP42003-P.
- To evaluate the effects of GWP42003-P on plasma concentrations of concomitant AEDs, if applicable.

Open-label Extension:

- To evaluate the long term effect of GWP42003-P on TAND, including cognitive and behavioral function and autistic features compared with placebo.

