Table 13.3.2	Shift Table for Biochemistry Laboratory Parameters – Based on Toxicity Limits	Safety Analysis Set
Table 13.3.3	Shift Table for eGFR – Based on Derived Grades	Safety Analysis Set
Table 13.4	Summary of Liver Parameter Flags	Safety Analysis Set
Table 13.5	Incidence of Laboratory Abnormalities	Safety Analysis Set
Table 13.6	Summary of Pregnancy Test and Urine THC Screen Results	Safety Analysis Set
Table 14.1.1	Summary of Vital Signs	Safety Analysis Set
Table 14.1.2	Incidence of Clinically Significant Changes from Baseline for Vital Signs	Safety Analysis Set
Table 14.1.3	Incidence of Defined Flagged Vital Signs	Safety Analysis Set
Table 14.1.4	Incidence of Vital Signs Abnormalities	Safety Analysis Set

Table Number	Title	Analysis Set
Table 14.2.1	Summary of ECG Parameters	Safety Analysis Set
Table 14.2.2	Incidence of Defined Flagged ECG Parameter Values	Safety Analysis Set
Table 14.2.3	Incidence of ECG Abnormalities	Safety Analysis Set
Table 14.3	Summary of Columbia-Suicide Severity Rating Scale by Type	Safety Analysis Set
Table 14.4	Incidence of Physical Examination Abnormalities	Safety Analysis Set
Table 14.5	Summary of Tanner Stages	Safety Analysis Set
Table 14.6	Summary of Menstruation Details	Safety Analysis Set
Table 14.7	Summary of Patients with Inpatient Hospitalizations due to Epilepsy	Safety Analysis Set
Table 14.8.1	Summary of Plasma Concentrations	Safety Analysis Set
Table 14.8.2.1	Summary of PK Parameters (Overall and by Age Group)	Safety Analysis Set
Table 14.8.2.2	Summary of PK Parameter Metabolite to Parent Ratio (Overall and by Age Group)	Safety Analysis Set
Table 14.9	Summary of Plasma Concentrations of Concomitant Antiepileptic Drugs	Safety Analysis Set
Table 14.10	Summary of Study Medication Use and Behavior Survey	Safety Analysis Set
Table 14.11.1	Summary of Supplemental Drug Accountability Form	Safety Analysis Set
Table 14.11.2	Summary of Supplemental Adverse Event Form	Safety Analysis Set
Table 14.11.3	Summary of Site Classification Form	Safety Analysis Set

Table 18 List of OLE Phase Tables

Table Number	Title	Analysis Set
OLE Table 1.1.1	Summary of Patient Disposition by Site	OLE Safety Analysis Set
OLE Table 1.1.2	Summary of Patient Disposition During by Country	OLE Safety Analysis Set
OLE Table 1.2	Summary of Overall Patient Disposition	OLE Safety Analysis Set
OLE Table 2	Summary of Important Protocol Deviations	OLE Safety Analysis Set
OLE Table 3.1	Summary of Demographic Data	OLE Safety Analysis Set

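### SAP 5.7.3 reports AED plasma levels only as raw values by arm and visit, which is likely to be imprecise and can understate an interaction where AED doses change after a rise

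*SAP*

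**What the plan says.** The blinded-phase exploratory objective is "To evaluate the effects of GWP42003-P on plasma concentrations of concomitant antiepileptic drugs (AEDs), if applicable" (Protocol 2.3, repeated in SAP 2.3). The matching endpoint is "Plasma concentrations of concomitant AEDs before and after treatment with GWP42003-P, where available" (Protocol 4.1.2, exploratory endpoints; SAP 3.3.3).

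Samples are scheduled before the IMP dose at Visits 3, 5, 7, 9 and 10 (Protocol 9.2.9.2), so a patient sampled at Visit 3 has a level from before any IMP.

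For analysis, Protocol 13.6.4 says "Where available, plasma concentrations of concomitant AEDs will be summarized". SAP 5.7.3 says "For each AED, plasma concentrations will be summarized by treatment arm at each visit for patients in the safety analysis set". Appendix 6 lists one table, 14.9, "Summary of Plasma Concentrations of Concomitant Antiepileptic Drugs", and one listing, 14.10. The plan specifies no change from Visit 3, no adjustment for AED dose, and no rule for samples taken after an AED dose change.

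On AED doses during the blinded phase, Protocol 8.2 requires them to stay stable and rests decisions on symptoms rather than levels, but also says "Concomitant AED dose reductions are permitted on clinical grounds". Protocol 9.2.9.2 says "AED doses should be adjusted, as appropriate, following discussion with the GW medical monitor in order to maintain stable AED plasma concentrations".

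**The concern.** The plan asks what the IMP does to AED levels, then tabulates levels without comparing each patient with himself or herself. Two weaknesses follow.

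- **Precision.** Patients aged 1 to 65 take different AEDs at different doses. Raw summaries at a visit carry all of that between-patient spread and reflect whoever is sampled at that visit.
- **Feedback.** If a level rises and the AED dose is then lowered, the later sample is pulled back toward its starting value and enters the visit summary unmarked. The patients with the clearest interaction can then look as if they had none.

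What is at stake is interpretation. Protocol 8.3 asks for care with CYP2C19 substrates and names N-desmethylclobazam. The SAP splits efficacy by use of four named AEDs (5.5.5) and liver flags by valproic acid and clobazam use (5.6.3.1). Reading those results is easier if it is known whether AED exposure changed.

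**Working it through.** The documents give no expected interaction, no rate of AED dose change and no precision for this endpoint, so there is no figure to reproduce. The text comes first, then illustrations on stated assumptions.

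**1. The same SAP treats comparable data differently.** Laboratory values (5.6.3.1), vital signs (5.6.4.1), ECG (5.6.4.2) and IGF-1 (5.6.4.6) all get change from baseline. For CBD and its metabolites, 5.7.2 dose-normalizes AUC and allows exclusion of samples affected by an IMP dose reduction. Section 5.7.3 has none of these for AEDs.

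**2. Precision.** On the log scale let σb be the between-patient SD, σw the within-patient SD and n the number per arm taking the AED. For a difference between arms at one visit:

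- raw levels: SE = √(σb² + σw²) × √(2/n)
- ratios to Visit 3: SE = √2 × σw × √(2/n)

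The paired SE is smaller exactly when σw < σb. Assume n = 20 and convert a CV by σ = √ln(1 + CV²):

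| Between CV / within CV | σb / σw | Raw SE | Paired SE | Reduction |
|---|---|---|---|---|
| 70% / 30% | 0.631 / 0.294 | 0.220 | 0.131 | about 40% |
| 50% / 40% | 0.472 / 0.385 | 0.193 | 0.172 | about 11% |
| 50% / 50% | 0.472 / 0.472 | 0.211 | 0.211 | none |

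**3. Attenuation.** Let R be the true active-to-placebo ratio at constant AED dose, f the share of active-arm patients whose AED dose is reduced, and c the fractional reduction. Assume that level is proportional to AED dose and that there are no reductions on placebo. Then:

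- ratio of arithmetic means = R(1 − fc), if reductions are unrelated to a patient's level
- ratio of geometric means = R(1 − c)^f, whoever is reduced

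| R | f | c | Arithmetic | Geometric |
|---|---|---|---|---|
| 2 | 0 | any | 2.00 | 2.00 |
| 2 | 10% | 25% | 1.95 | 1.94 |
| 2 | 20% | 50% | 1.80 | 1.74 |
| 2 | 30% | 50% | 1.70 | 1.62 |
| 2 | 50% | 50% | 1.50 | 1.41 |
| 1.25 | 30% | 50% | 1.06 | 1.02 |

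For example, 2 × (1 − 0.2 × 0.5) = 1.80 and 2 × 0.5^0.2 = 1.74. On the arithmetic scale, the R = 2 rows with reductions lose 5% to 50% of the excess over 1, and the R = 1.25 row loses 75%. If f and c are equal in both arms, the between-arm ratio is unbiased, but the before-and-after change within each arm is still lowered.

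**4. Would dropping post-change samples cure this?** Take R = 2 with log ratios normal with SD s. As an extreme case, suppose the AED dose is halved in the share p of patients with the largest rises. The geometric mean ratio among the rest is exp(ln 2 − s·φ(z)/(1 − p)), where φ is the standard normal density and z its (1 − p) quantile. With all samples kept it is 2^(1 − p).

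| p | All samples | Restricted, s = 0.3 | s = 0.4 | s = 0.5 |
|---|---|---|---|---|
| 25% | 1.68 | 1.76 | 1.69 | 1.62 |
| 50% | 1.41 | 1.57 | 1.45 | 1.34 |
| 75% | 1.19 | 1.37 | 1.20 | 1.06 |

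Restriction removes the patients who rose most. It can therefore be as biased as keeping every sample, or more so.

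**5. Dose normalization.** Under proportionality a patient's later level is R(1 − c) times the Visit 3 level, at (1 − c) times the Visit 3 AED dose. The ratio of level per unit dose is R(1 − c)/(1 − c) = R, so the effect is recovered.

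**The case against.** The strongest reply is that this is a modest exploratory summary and is adequate as one. The objective applies only where applicable, the endpoint only where data exist, and Protocol 13.6.4 promises no more than a summary. Table 14.9 would show Visit 3 beside later visits with a placebo arm. SAP 5.1 adds the median and range, Listings 14.10 and 6.3 give individual levels and AED use, and SAP 5.3 lets changes from baseline be added to listings. AED doses are meant to stay stable (Protocol 8.2), and dosage changes are listed as prohibited (8.3).

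Much of this stands. It limits the size of the problem and settles its priority as low. It does not supply the missing comparison. A by-visit table of raw levels gives no within-patient change and no confidence interval for one, and listings are not a summary by arm. The subgroup analyses in SAP 5.5.5 use AED use (yes or no), not AED exposure.

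Two further points stand against the illustrations. Samples are timed to the IMP dose and not to the AED dose, so a low within-patient CV is not assured. Also, the reductions allowed in Protocol 8.2 include those for transaminase elevations, which need not fall on the patients whose AED level rose most.

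A reader might infer that the planned analysis does understate the interaction because AED doses are cut when levels rise. The documents do not support that. Protocol 8.2 rests decisions on symptoms, while 9.2.9.2 speaks of adjusting doses, not only lowering them, to keep levels stable. The two sections conflict, and no frequency is given.

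**Conclusion.** The point holds as a minor improvement. The planned summary does not use the paired comparison that the endpoint describes. A paired one is more precise whenever within-patient variability is below between-patient variability, which is likely but not shown in the documents. The raw summary can understate an interaction where AED doses are reduced after a rise. The size is unknown and is zero if no AED dose changes. Samples taken before any change are unaffected. Every figure above rests on assumed CVs, numbers per arm, shares reduced and dose proportionality.

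Three further inferences should be resisted:

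- **That restricting to samples before any AED dose change should be the main analysis.** It can itself be selective, as step 4 shows.
- **That AED metabolites are measured.** Neither Protocol 9.2.9.2 nor SAP 5.7.3 says so; the mention of N-desmethylclobazam in Protocol 8.3 is a caution, not an assay plan.
- **That the efficacy conclusions are at risk.** No test in the SAP 5.5.1 hierarchy uses AED levels.

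**What to change.** In SAP 5.7.3, for each AED assayed and any metabolite actually assayed:

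1. Add the within-patient ratio of each post-baseline level to the Visit 3 pre-dose level, as geometric mean ratios with 95% confidence intervals by arm and visit, using all samples.
2. Beside it, show the same ratio with each level divided by the AED dose in use at that sample. Count separately any patient who has stopped that AED, since no normalized value exists.
3. Tabulate AED dose changes by arm and visit, and flag in Listing 14.10 the samples taken after a change.
4. Show a summary restricted to samples before any AED dose change, if at all, as supportive only, with a note that it can be selective.

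Separately, Protocol 8.2 and 9.2.9.2 must be reconciled on whether AED levels drive AED dose changes. No view is taken here on which should prevail.

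The cost is one SAP paragraph and one or two tables. Concentrations are already collected, and Protocol 9.2.5 already requires medication changes to be recorded in the CRF. The main drawback is that the normalized version relies on dose proportionality, which the documents do not establish for any AED. Showing it beside the unadjusted ratio lets the reader see how much depends on it.

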5.7.4 Study Medication Use and Behavior Survey

This form consists of 18 questions regarding the use of the IMP. The trained investigator or trial coordinator will complete this survey as an interview with the patient/caregiver at the final dosing visit.

The form will be completed for all patients 12 years of age and older in the trial.

Each question will be summarized, on a categorical scale, by treatment arm. Percentages will be based on the number of patients completing the survey, in each treatment arm. The summary will be presented separately for all patients with a completed form and patients 12 years of age and older.

5.7.5 Supplemental Drug Accountability Form

This form consists of 7 questions regarding various aspects of drug accountability and patient usage. It is completed as part of an interview with the patient/caregiver when a triggering drug accountability discrepancy is identified.

The triggering drug accountability discrepancies are as follows:

- Missing bottle(s).
- Compliance issues where one or more bottles are used compared to what was the expected use, according to the IVRS report and paper diary.
- Returned IMP supply with evidence of tampering.
- Greater than the target daily dose as recorded in the IVRS report and paper diary.

The number of patients with a completed form will be summarized separately for the blinded phase and OLE phase. The summary will be presented separately for all patients with a completed form and patients 12 years of age and older.

5.7.6 Supplemental Adverse Event Form

This form consists of 15 questions regarding the AE and use of IMP. It is completed as part of an interview with the patient/caregiver when a triggering AE of interest is reported.

The categories for triggering AEs of interest are:

- Euphoria or inappropriate elation.
- Inappropriate laughter or exhilaration.
- Mood changes.
- Drunk, high or intoxicated.
- Hallucinations (visual or auditory), dissociations, disorientation, agitation.
- Disturbance in cognition, memory, or attention.
- Drug abuse.
- Drug withdrawal or drug withdrawal syndrome.
- Addiction.
- Overdose.
- Misuse of IMP.
- Thoughts of suicide, attempted suicide or suicide.

The number of patients with a completed form will be summarized separately for the blinded phase and OLE phase. The summary will be presented separately for all patients with a completed form and patients 12 years of age and older.

5.7.7 Site Classification Form

The investigator reviews the applicable Supplemental Adverse Event Form or Supplemental Drug Accountability Form, and then completes a Site Classification Form. For each Supplemental Adverse Event Form or Supplemental Drug Accountability Form completed, there should be an associated Site Classification Form.

The Site Classification Form requires the investigator to assign the finding to an appropriate classification and then to also assign the possible relationship to the IMP. The investigator is also required to indicate the level of the certainty of the classification.

The number of patients with a completed form a will be summarized, along with the form associated to, separately for the blinded phase and OLE phase. The summary will be presented separately for all patients with a completed form and patients 12 years of age and older.

5.7.8 IVRS Compliance

For the blinded phase only, the number of unreported days in IVRS, during the baseline and treatment periods, will be summarized, on a continuous and categorical scale, by treatment arm for patients in the ITT analysis set. For the summary on a continuous scale, the lower and upper quartiles will also be presented.

The percentage IVRS compliance, during the baseline and treatment periods, will also be summarized, on a continuous and categorical scale, and calculated as:

$$(\text{Number of reported days in IVRS} \div (\text{Number of reported days in IVRS} + \text{Number of unreported days in IVRS})) \times 100$$

5.8 Changes in the Conduct of the Trial or Planned Analysis

During the OLE, seizure counts are collected every 7 days rather than daily. Hence, the endpoint of TSC-associated seizure free days has been defined for the blinded phase only.

The endpoint of number of patients experiencing a >25% worsening, -25 to +25% no change, 25–50% improvement, 50–75% improvement or >75% improvement in convulsive seizures from baseline has been updated to the following:

- Number of patients experiencing a >25% increase, ≥ 0 to $\leq 25\%$ increase, >0 to $<25\%$ reduction, ≥ 25 to $<50\%$ reduction, ≥ 50 to $<75\%$ reduction or $\geq 75\%$ reduction in convulsive seizures from baseline.

7. AMENDMENTS

Notable changes to the SAP that were completed prior to unblinding, are given below. Minor changes, clarifications and corrections are not listed.

Date	Section	Description of Change
24Apr2019	5.5.1	The hierarchy for analysis was updated to be consistent with protocol version 8, dated 23 rd April 2019.

8. ATTACHMENTS AND APPENDICES

Appendix 1 Adverse Events of Special Interest – Abuse Liability

Withdrawal	Drug withdrawal convulsions Drug withdrawal headache Drug withdrawal maintenance therapy Drug withdrawal syndrome Drug withdrawal syndrome neonatal Drug rehabilitation Rebound effect Steroid withdrawal syndrome Withdrawal arrhythmia Withdrawal syndrome
Drug abuse and dependence	Dopamine dysregulation syndrome Drug abuse Drug abuser Drug dependence Drug dependence, antepartum Drug dependence, postpartum Intentional drug misuse Intentional overdose Maternal use of illicit drugs Neonatal complications of substance abuse Polysubstance dependence Substance abuse Substance abuser Accidental overdose Dependence Disturbance in social behaviour Drug administered at inappropriate site Drug detoxification Drug diversion Drug level above therapeutic Drug level increased Drug screen Drug screen positive Drug tolerance Drug tolerance decreased Drug tolerance increased Medication overuse headache Narcotic bowel syndrome Needle track marks Overdose Prescribed overdose Prescription form tampering Substance use Substance-induced mood disorder Substance-induced psychotic disorder Toxicity to various agents

Appendix 2 Ranges for Clinically Significant Changes and Other Defined Flagged Values in Vital Signs

The range of values that will be used to identify clinically significant changes in vital signs parameters (See Section 5.6.4.1) are presented in Table 9.

Table 9 Ranges for Clinically Significant Changes in Vital Signs

Vital Sign	Range
Sitting Systolic BP	Change: < -20, > 20
Sitting Diastolic BP	Change: < -10, > 10
Pulse Rate	Change: < -10, > 10
Weight	Percent Change: $\leq -7, \geq 7$

Defined flagged values that will be used to identify low or high vital signs parameters (See Section 5.6.4.1) are presented in Table 10.

Table 10 Other Defined Flagged Values for Vital Signs

Vital Sign	Flag
Sitting Systolic BP	< 90, > 140, > 160
Sitting Diastolic BP	< 50, > 90, > 100
Pulse Rate	< 60, > 100
Temperature	> 38.0, < 36.0
Respiratory Rate	< 12, > 20

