## 6.1 Inclusion Criteria

For inclusion in the study, patients must fulfil ALL of the following criteria:

- 6.1.1 Patient is male or female aged between one and 65 years inclusive.
- 6.1.2 Patient and/or parent(s)/legal representative is willing and able to give informed consent/assent for participation in the study (see Section 15.2).
- 6.1.3 Patient and their caregiver are willing and able (in the investigator's opinion) to comply with all study requirements (including accurate diary and IVRS completion).
- 6.1.4 Well-documented clinical history of epilepsy, which is not completely controlled by their current AEDs.
- 6.1.5 Clinical diagnosis of TSC according to the criteria agreed by the 2012 International Tuberous Sclerosis Complex Consensus Conference.
- 6.1.6 Taking one or more AEDs at a dose which has been stable for at least four weeks prior to screening.
- 6.1.7 All medications or interventions for epilepsy (including ketogenic diet and any neurostimulation devices for epilepsy) must have been stable for one month prior to screening and the patient is willing to maintain a stable regimen throughout the study.
- 6.1.8 Patient is willing to keep any factors expected to affect seizures stable (such as the level of alcohol consumption and smoking).
- 6.1.9 Patient and/or parent(s)/legal representative is willing to allow the responsible authorities to be notified of participation in the study, if mandated by local law.

6.1.10 Patient and/or parent(s)/legal representative is willing to allow his or her primary care practitioner and consultant (if they have one) to be notified of participation in the study, if mandated by local law.

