## 7.2 Randomization

The allocation of IMP to treatment number will be done according to a randomization schedule produced by an independent statistician. The randomization schedule will be held centrally and not divulged to any other person involved in the study until the database has been locked and unblinding authorized by the relevant GW personnel. For access to blinded treatment assignment, see Section 8.5.

The randomization will be stratified by age group (1–6 years, 7–11 years, 12–17 years and 18–65 years).

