5.1.3 Definitions

5.1.3.1 Baseline

For clinic visit based endpoints, baseline is defined as the last record or measure collected prior to the first dose of IMP.

For IVRS based endpoints, baseline will include all available data from the day of Visit 2 to Day 1 of the blinded phase.

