Shift tables for hematology and biochemistry parameters will be constructed, based upon normal ranges and GW toxicity limits (See Section 8), to determine the categorical shifts from baseline to each post-baseline visit. Values will be categorized as 'Normal', 'Low' or 'High' based on normal ranges and 'Toxicologically Low', 'Toxicologically Normal' or 'Toxicologically High' based on GW toxicity limits.

For eGFR, results will be assigned to the following grades:

- Normal: $>60 \text{ ml/min}/1.73 \text{ m}^2$
- Grade 1: $60 \text{ ml/min}/1.73 \text{ m}^2$
- Grade 2: $\geq 30 \text{ and } < 60 \text{ ml/min}/1.73 \text{ m}^2$
- Grade 3: $\geq 15 \text{ and } < 30 \text{ ml/min}/1.73 \text{ m}^2$
- Grade 4: $< 15 \text{ ml/min}/1.73 \text{ m}^2$

A separate shift table will be produced for eGFR based upon the above grades to determine the categorical shifts from baseline to each post-baseline visit.

For the blinded phase, scatter plots will be produced for each laboratory parameter presenting the maximum post baseline result divided by the upper limit of normal (ULN) on the Y-axis, and the baseline result divided by the ULN on the X-axis. However, for prothrombin international normalized ratio (INR), both axes will present the raw results rather than dividing by ULN.

An additional table will be produced for the blinded phase only, summarizing the number of patients meeting the following criteria:

- Alanine aminotransferase (ALT) $> 1 \times \text{ULN}$ at baseline
- Aspartate aminotransferase (AST) $> 1 \times \text{ULN}$ at baseline
- AT $> 1 \times \text{ULN}$ at baseline
- Treatment emergent ALT $> 3 \times \text{ULN}$, $> 5 \times \text{ULN}$ and $> 8 \times \text{ULN}$
- Treatment emergent AST $> 3 \times \text{ULN}$, $> 5 \times \text{ULN}$ and $> 8 \times \text{ULN}$
- Treatment emergent AT $> 3 \times \text{ULN}$, $> 5 \times \text{ULN}$ and $> 8 \times \text{ULN}$
- Treatment emergent AT $> 3 \times \text{ULN}$ and either bilirubin $> 2 \times \text{ULN}$ or INR > 1.5

where AT is AST or ALT, and treatment emergent is defined as criteria not met at baseline but met at any time post-baseline. The above will be summarized overall and for the following subgroups:

- Sex (Male, Female).

- Valproic acid use (Yes, No).
- Clobazam use (Yes, No).
- Valproic acid use and Clobazam use (Yes/Yes, Yes/No, No/Yes, No/No).
- Patients taking 3 or more current AEDs.
- Patients taking 4 or more current AEDs.

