5.6.4 Vital Signs, Other Physical Findings and Other Safety Data

5.6.4.1 Vital Signs

At Visit 1, 3 and B3, systolic and diastolic blood pressure are collected in the sitting, supine and standing positions. At all other visits, systolic and diastolic blood pressure are collected in the sitting position only.

Summaries will be presented by treatment arm for each vital sign parameter at each visit. Change from baseline to each post-baseline visit will also be presented.

Body mass index will be calculated, for each visit in which height and weight are recorded, as:

$$\text{Weight (kg)} \div \text{height (m)}^2$$

A separate table will be produced, by treatment arm and visit, presenting the incidence of patients with vital signs indicative of a medical condition at Visit 1 and indicative of an adverse event after Visit 1.

Based on the criteria presented in Section 8, clinically significant changes from baseline in vital signs measurements and other defined flagged values will be identified at each visit. The number of patients with a clinically significant change from baseline will be summarized by parameter, visit and treatment arm. The number of patients with at least one post-baseline flagged vital sign parameter value will be summarized by parameter, flagged criteria and treatment arm for the blinded phase and repeated for the OLE phase.

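### Vital-sign flags use one set of absolute limits for ages 1 to 65 and count patients already flagged at baseline; the 7% weight rule is insensitive to failure to gain

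*SAP*

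**What the plan says.** Protocol 6.1.1 sets the age range: "Patient is male or female aged between one and 65 years inclusive". Protocol 7.2 stratifies randomization into four age groups: 1–6, 7–11, 12–17 and 18–65 years.

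SAP Appendix 2 has two tables, neither split by age.

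- **Table 9** lists changes from baseline regarded as clinically significant: sitting systolic BP by more than 20, sitting diastolic BP and pulse by more than 10, and weight by 7% or more, in either direction.
- **Table 10** is introduced as follows: "Defined flagged values that will be used to identify low or high vital signs parameters (See Section 5.6.4.1) are presented in Table 10". Its limits are absolute: systolic BP below 90, above 140 or above 160; diastolic BP below 50, above 90 or above 100; pulse below 60 or above 100; temperature above 38.0 or below 36.0; respiratory rate below 12 or above 20.

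SAP 5.6.4.1 counts them differently. For Table 9: "The number of patients with a clinically significant change from baseline will be summarized by parameter, visit and treatment arm". For Table 10: "The number of patients with at least one post-baseline flagged vital sign parameter value will be summarized by parameter, flagged criteria and treatment arm". The Table 10 count is made in the blinded phase and again in the open-label extension (OLE). The reference for change is in SAP 5.1.3.1: "For clinic visit based endpoints, baseline is defined as the last record or measure collected prior to the first dose of IMP". OLE weight changes therefore also run from the pre-randomization value.

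For its liver table, SAP 5.6.3.1 adds a condition that Table 10 lacks: "treatment emergent is defined as criteria not met at baseline but met at any time post-baseline".

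**The concern.** An absolute limit applied from age 1 to age 65 cannot suit every age. If it is routinely exceeded by healthy young children, and one exceedance at any visit is enough, many patients in every arm will be counted for reasons unrelated to treatment. A drug effect then has to show among the remaining patients, so the difference in SAP Table 14.1.3 is smaller than the effect among those who could newly cross a limit. In OLE Table 14.1.3 everyone is on drug and columns show only prior treatment and the total, so no concurrent control indicates how much is background.

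Weight raises a separate issue. Growth in patients under 18 is a secondary objective (Protocol 2.2). A percentage change from a fixed starting weight treats normal growth as gain, and treats a child whose weight stands still as unchanged.

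**Working it through.** The plan gives no figure for these tables, so there is none to reproduce.

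**1. Comparison within the SAP.** The liver table (5.6.3.1) counts only criteria not met at baseline. The eGFR formula changes at 18 years (5.6.3.1), and so does the automated lymphocyte limit (Appendix 4, Table 13). Table 10 has neither a baseline condition nor an age split. Table 9 has no age split, but it is referenced to baseline throughout.

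**2. Chance of at least one flag.** Protocol Appendix 1 schedules vital signs at six on-treatment visits of the blinded phase (4, 5, 6, 7, 9, 10). If a value lies outside a limit with probability p at each visit, independently, the chance of at least one flag is 1 − (1 − p)^6: 26.5% at p = 0.05, 46.9% at 0.10, 73.8% at 0.20, 88.2% at 0.30 and 98.4% at 0.50. If the same children exceed the limit at every visit, the chance is simply p. Real data lie between these extremes.

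The means and SDs below are assumptions, not figures from the documents. They use a normal distribution with cut-offs at 100.5 and 20.5 because readings are whole numbers.

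| Assumed mean/SD | p per visit | At least one of 6, independent |
|---|---|---|
| Pulse 80/10 | 2% | 12% |
| Pulse 95/10 | 29% | 87% |
| Pulse 105/12 | 65% | >99% |
| Respiratory rate 16/2 | 1% | 7% |
| Respiratory rate 20/2.5 | 42% | 96% |
| Respiratory rate 22/3 | 69% | >99% |

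**3. Dilution.** Let b be the background proportion flagged in every arm and e the extra proportion the drug would flag among the others. The observed difference is (1 − b) × e. With e = 15 points: 0.95 × 15 = 14.3 at b = 5%; 0.70 × 15 = 10.5 at 30%; 0.40 × 15 = 6.0 at 60%; 0.10 × 15 = 1.5 at 90%.

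**4. What a baseline condition recovers.** If background flags persist within a child, they are present at baseline, and excluding them restores the full 15 points among patients at risk. If they come and go independently, it helps little: at p = 0.20, 73.8% of those clear at baseline would still be flagged later. In that case age-appropriate limits do the work, which is why the fix has both parts.

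**5. Weight.** The OLE starts on the day of Visit 10, 112 days after randomization, and Visit B10 is 364 days later: 112 + 364 = 476 days, or 68 weeks. If normal growth since baseline is g, the loss flag first fires at a shortfall against expected weight of 1 − 0.93/(1 + g). Assume a 15 kg child gaining 2 kg a year (not in the documents):

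- Week 16: 2 × 112/365.25 = 0.61 kg, so g = 4.1%. Shortfall at the flag: 1 − 0.93/1.041 = 10.7%.
- B10: 2 × 476/365.25 = 2.61 kg, so g = 17.4%. Shortfall at the flag: 1 − 0.93/1.174 = 20.8%.
- The same child with no gain at all by B10 is 1 − 1/1.174 = 14.8% below expected weight, with a recorded change of 0% and no flag.

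Over a range of g, the shortfall needed is 8.8% at g = 2%, 12.3% at 6%, 15.5% at 10% and 22.5% at 20%.

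The gain flag fires on growth alone once g reaches 7%. That needs 7 × 52/16 = 22.8% a year by week 16, but only 7 × 52/68 = 5.4% a year by week 68.

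**The case against.** The strongest reply is that these tables are supplementary. SAP 5.6.4.1 first summarizes every vital sign by arm and visit with change from baseline, adds BMI, and separately reports vital signs indicative of an adverse event. Height and weight are summarized and listed (5.6.4.3). Protocol 13.6.5.4 asks only for summaries and changes. No test is planned on the flags. Randomization is stratified by age, so background flags should be roughly balanced. The any-post-baseline count also matches the ECG flags (5.6.4.2). All of this stands, and it sets the severity.

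It is also right that BP and pulse have baseline-referenced criteria in Table 9, so an effect on them has another route to notice. Among the Table 10 items, only respiratory rate and temperature lack one.

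Several stronger readings are tempting but not supported:

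- *Appendix 2 ignores baseline altogether.* This is true of the Table 10 count only; all of Table 9, including weight, is change from baseline.
- *Weight loss in growing children is hidden.* A true fall of 7% below baseline is flagged at any age and any visit. What the rule misses is failure to gain, and loss that follows growth.
- *The flags favour one arm.* Background flags fall in all arms, so the effect is dilution, not bias.
- *OLE weight gains will be mostly growth.* The documents give neither the age mix nor growth rates, and adults up to 65 are enrolled.

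**Conclusion.** The point stands as a minor one. It is certain from the text that Table 10 applies one set of limits to ages 1 to 65 and that its count has no baseline condition, although the SAP uses both refinements elsewhere. How many young children would be flagged is not certain: it depends on paediatric resting values the documents do not give and on how far a child's readings agree between visits. Under the assumptions shown, the proportion flagged at least once runs from about 7% to nearly all. The loss of contrast is correspondingly negligible or severe, and matters most for respiratory rate and temperature.

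For weight, the insensitivity is modest in the 16-week randomized comparison and larger by the end of the OLE, where normal growth can also trigger the gain flag. The size rests on the assumed 15 kg child gaining 2 kg a year. Efficacy, type I error and sample size are untouched.

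**What to change.** - In SAP 5.6.4.1 and in Tables 14.1.3 and OLE 14.1.3, add a count of patients newly flagged after baseline, using the rule the SAP already applies to liver tests.
- Report that count by the four randomization age strata, with age-appropriate limits for patients under 18.
- For patients under 18, add an age- and sex-standardized weight change (z-score) beside the 7% rule, which can stay.

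No new data are needed. The newly flagged count and the stratum split need only programming. The limits under 18 and the z-scores also need a published reference table, to be named in Appendix 2 before unblinding. Splitting by stratum makes the cells smaller, which is acceptable in a descriptive table.
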